7 CONCOMITANT MEDICATIONS AND OTHER RESTRICTIONS

7.1 Concomitant Medications

All concomitant medications, including all prescription and over-the-counter drugs, supplements, and intravenous medications and fluids, taken by or administered to the patient within 28 days before Day 1 should be recorded in the source documents and eCRF.

The PI will instruct the patient to notify the study site about any new medical treatment taken during the Extension Phase.

7.1.1 Core Phase

Patients will refrain from use of any prescription or nonprescription medications/products during the study through the EOT Visit, unless the investigator and/or sponsor have given their prior consent.

Acetaminophen (2 g/day for up to 3 consecutive days) is an acceptable concomitant medication. Acetaminophen can be taken as specified above at any time relative to the administration of study drug. The administration of any other concomitant medications during the study is prohibited without prior approval of the investigator, unless its use is deemed necessary in a medical emergency. Any medication taken by a subject during the course of the study and the reason for its use will be documented in the source data.

7.1.1.1 Diet

While confined at the study site, patients will receive a standardized diet at scheduled times that do not conflict with other study-related activities.

Foods and beverages containing poppy seeds, grapefruit, or Seville oranges will not be allowed from 72 hours prior to Check-in (Day -1) until discharge on Day 12 (Part A) and Day 9 (Part B).

Caffeine-containing foods and beverages will not be allowed from 72 hours prior to Check-in (Day -1) until discharge on Day 12 in Part A and Day 9 in Part B.

Consumption of alcohol will not be permitted from 72 hours prior to Check-in (Day -1) until discharge on Day 12 (Part A) and Day 9 (Part B), and alcohol intake will be limited to a maximum of 2 units/day on all other days while patients are not in the CRU, from Screening through the EOT Visit (end of Core Phase).

On days 3 to 9 and 11, patients should be given rifampin in the fasted state (at least 2 hours); patients should continue to fast for 1h postdose.

On Days 3 to 6 and 8, patients should be given itraconazole 30 minutes after a meal.

7.1.1.2 Smoking

Use of tobacco- or nicotine-containing products will not be permitted from Screening until the EOT Visit (end of Core Phase).

7.1.1.3 Exercise

Patients are required to refrain from strenuous exercise from 72 hours before Check-in (Day -1) until the EOT Visit (end of Core Phase) and will otherwise maintain their normal level of physical activity during this time (ie, will not begin a new exercise program nor participate in any unusually strenuous physical exertion).

7.1.1.4 Blood Donation

Patients are required to refrain from donation of blood from 56 days prior to Screening, plasma from 30 days prior to Screening, or platelets from 6 weeks prior to Screening until 3 months after the EOT Visit (end of Core Phase).

7.1.2 Extension Phase

Supportive therapy considered necessary for the patients' welfare may be given at the discretion of the PI. This includes, but is not limited to analgesics, anticonvulsants, anti-emetics, antidiarrheal treatment, laxatives, opiates, and transfusion of blood products.

7.1.2.1 Prohibited Medications

Patients are not allowed to receive other anticancer therapy, including surgery; radiation therapy; immunotherapy; investigational agents; cytotoxic, biologic, or hormone therapy; anticancer Chinese medicine; or herbal remedies ≤ 14 days (or ≤ 5 half-lives, if applicable) before Day 1 of the Core Phase and during the study, including the Extension Phase. Hormone replacement therapy use is allowed during the Extension Phase.

Use of bisphosphonate and denosumab is permitted if the patient had already been receiving it at a stable dose > 28 days before Day 1.

The primary metabolic pathway for pamiparib involves the CYP3A isoform. Administration of strong/moderate inhibitors of CYP3A or strong CYP3A inducers is not allowed during the Core and Extension Phase.

Please refer to the drugs/substances listed in [Appendix 6](#) and to <http://medicine.iupui.edu/clinpharm/ddis/main-table/> for a more complete list of medications that are not allowed. Consumption of grapefruit and Seville oranges or their juices are not allowed throughout the study. No other dietary restrictions will apply.

7.1.2.2 Medications to Be Used with Caution (Core and Extension Phases)

Based on preliminary in vitro screening assays, pamiparib is not a strong inhibitor of other human CYP isoenzymes tested. It is a moderate inhibitor of CYP2C9 ($IC_{50} = 6.48 \mu M$). Investigators need to be aware that pamiparib has the potential to interfere with the appropriate metabolism of medications that rely on CYP2C9 and follow the prescribing information recommendations for use with CYP2C9 inhibitors. Therefore, careful monitoring should be used when co-prescribing CYP2C9 substrates with a narrow therapeutic index, such as phenytoin and warfarin.

Examples of these medications are listed in [Appendix 6](#) and these should be used cautiously with drug concentration monitoring where appropriate.

In addition to CYP3A, pamiparib can also be metabolized by [REDACTED] in human liver microsomes, but to a lesser extent. See [Appendix 6](#) for medications that should be used with caution for that reason.

7.2 Contraception

Please refer to [Appendix 4](#).

8 STUDY ASSESSMENTS AND PROCEDURES

Every effort will be made to schedule and perform the procedures as closely as possible to the nominal time, giving considerations to appropriate posture conditions, practical restrictions, and the other procedures to be performed at the same timepoint.

The order of priority for scheduling procedures around a timepoint is (in descending order of priority):

- dosing
- blood samples
- any other procedures (ECGs will be scheduled before vital sign measurements)

8.1 Pharmacokinetic Assessments (Core Phase ONLY)

8.1.1 Pharmacokinetic Blood Sample Collection and Processing

Blood samples (approximately 1 x 2 mL for pamiparib) will be collected by venipuncture or cannulation at the times indicated in the Schedule of Assessments in [Appendix 1](#). Procedures for collection, processing, and shipping of PK blood samples will be detailed in the laboratory manual. Plasma samples remaining after bioanalysis of pamiparib may be used to qualitatively or quantitatively characterize any metabolites of pamiparib.

8.1.2 Analytical Methodology

Plasma concentrations of pamiparib will be determined using a validated analytical procedure. Specifics of the analytical method will be provided in a separate document.

8.2 Safety and Tolerability Assessments (Core and Extension Phases)

8.2.1 Adverse Events

Adverse event definitions, assignment of severity and causality, and procedures for reporting SAEs are detailed in [Section 9](#). The condition of each patient will be monitored from the time of signing the Informed Consent Form (ICF) to the end of the study. Patients will be observed for any signs or symptoms and asked about their condition by open questioning, such as “How have you been feeling since you were last asked?” at least once each day while a resident at the study site and at each study visit. Patients will also be encouraged to spontaneously report AEs occurring at any other time during the study. Any AEs, SAEs, and remedial action required will be recorded in the patient’s source data. The nature, time of onset, duration, and severity will be documented, together with a PI’s (or designee’s) opinion of the relationship to study drug. Adverse events recorded during the course of the study will be followed-up, where possible, until resolution. This will be completed at the PI’s (or designee’s) discretion.

8.2.2 Clinical Laboratory Evaluations

Blood and urine samples will be collected for clinical laboratory evaluations (including clinical chemistry, hematology, urinalysis, and serology) at the times indicated in the Schedule of Assessments in [Appendix 1](#). Clinical laboratory evaluations are listed in [Appendix 7](#). Blood volume required is listed in [Appendix 8](#).

Patients will be asked to provide urine samples for a drugs of abuse screen and undergo an alcohol breath test at the times indicated in the Schedule of Assessments in [Appendix 1](#). For all female subjects, a pregnancy test will be performed at the times indicated in the Schedule of Assessments in [Appendix 1](#).

The Investigator (or designee) will perform a clinical assessment of all clinical laboratory data.

8.2.3 Vital Signs

Supine blood pressure, supine pulse rate, respiratory rate, and body temperature will be assessed at the times indicated in the Schedule of Assessments in [Appendix 1](#). Vital signs may also be performed at other times if judged to be clinically appropriate or if the ongoing review of the data suggests a more detailed assessment of vital signs is required.

All measurements will be performed singly and repeated once if outside the relevant clinical reference range.

Patients must be supine for at least 5 minutes before blood pressure, heart rate, and temperature measurements. During the in-house period of the Core Phase, blood pressure, heart rate, and temperature measurements should be conducted in the morning. When scheduled at the same time, vital sign assessments are to be performed prior to PK blood draws, with blood draws to occur as close to the nominal times as possible except for Screening and Day -1.

8.2.4 12-Lead Electrocardiogram

Resting 12-lead ECGs will be recorded after the patient has been supine and at rest for at least 5 minutes at the times indicated in the Schedule of Assessments in [Appendix 1](#).

Single 12-lead ECGs will be repeated once if either of the following criteria apply postdose:

- QTcF > 500 msec
- QTcF change from the baseline (predose) is > 60 msec

Additional 12-lead ECGs may be performed at other times if judged to be clinically appropriate or if the ongoing review of the data suggests a more detailed assessment of ECGs is required. The investigator (or designee) will perform a clinical assessment of each 12-lead ECG. When numerous assessments are scheduled at the same time, ECGs are to be performed prior to vital sign assessments and PK blood draws, with PK blood draws to occur as close to the nominal times as possible except for Screening and Day -1.

8.2.5 Physical Examination

Complete and limited physical examinations will be performed at the timepoints specified in the Schedule of Assessments in [Appendix 1](#). A complete physical examination includes a review of the following systems: head/neck/thyroid; eyes/ears/nose/throat; respiratory; cardiovascular; lymph nodes; abdomen; skin; musculoskeletal; and neurological. A limited physical examination includes an assessment of the patient's general appearance, skin, thorax/lungs, cardiovascular, and abdomen.

8.2.6 Tumor Assessments

Tumor imaging (CT or magnetic resonance imaging [MRI], with preference for CT) will be performed at Screening and every 8 weeks (± 7 days) or as per standard of care. At the PI's discretion, CT or MRI scans may be repeated at any time if disease progression (PD) is suspected. The same imaging technique should be used for each patient throughout the study.

8.3 End-of-Treatment Visit

EOT Visit should occur within 7 days after the last dose of rifampin/itraconazole (Core Phase) or pamiparib (Extension Phase). Required assessments are listed in [Appendix 1](#). A visit should be scheduled as soon as possible, but the EOT Visit may occur later after discussion with the medical monitor for specific circumstances, such as prolonged hospitalization. During the Extension Phase, the visit at which tumor assessments showed PD may be used as the EOT visit providing all required assessments were performed. Tumor assessments do not have to be repeated if they were performed within 14 days of the EOT visit, or at a prior response evaluation that documented PD. An ECG does not have to be repeated if it was performed within 14 days of the EOT visit.

8.4 Safety Follow-up Visit/Call

The Safety Follow-Up visit will occur 30 days (± 7 days) after the last dose of study drug or before initiation of new anticancer therapy, whichever occurs first. The Safety Follow-up in the Core Phase is only to be conducted if the patient does not continue to the Extension Phase. If new anticancer therapy is inadvertently initiated before the Safety Follow-up Visit, (eg, without the knowledge of the study center team), a Safety Follow-up Visit should be scheduled as soon as possible. For patients who do not want to or cannot return to the clinic for the Safety Follow-up Visit, the patient should be contacted by telephone for a review of AEs. If these attempts of contact are unsuccessful, the additional attempts detailed in [Section 9.1.4](#) should be made.

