9.3 Timing, Frequency, and Method of Capturing Adverse Events and Serious Adverse Events

9.3.1 Adverse Event Reporting Period

After the ICF has been signed but prior to the administration of the study drug, only SAEs should be reported to the sponsor.

After initiation of study drug, all AEs and SAEs, regardless of relationship to pamiparib or placebo, will be reported until 30 days after the last dose of study drug or initiation of new anticancer therapy, whichever occurs first. After this period, the investigator should report any SAEs that are believed to be related to prior study treatment.

After a patient is discontinued from the study, investigators are not obligated to actively seek AEs or SAEs from the former patient. However, if the investigator learns of any SAE, including a death, at any time, and considers the SAE related to pamiparib, the investigator will notify the sponsor.

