14 APPENDICES

Appendix 1: Schedule of Assessments

Schedule of Assessments: Part A

Study Procedures	Screening		Core Phase				Safety Follow-up Visit (≤30 days after last dose) ^p
	Days -28 to -1 ⁿ	Day -1	Day 1	Days 2 to 11	Day 12	Core Phase EOT Visit (≤7 days after last dose)	
Informed consent	X						
Inclusion/exclusion criteria	X						
Confirm eligibility (laboratory values) ^a		X					
Demographic data ^b	X						
Medical history ^c	X						
ECOG Performance Status	X						
Urine drug screen	X	X					
Alcohol breath test	X	X					
Serum pregnancy test/FSH ^d	X (Days -7 to -1)						
Height, BMI ^e	X						
Weight	X	X			X		
Serology (HBV, HCV) ^f	X						
Study residence							
Check-in		X					
Check-out					X ^o		
Non-residential visit						X	
Study drug administration ^g							
Pamiparib Dosing			X	Day 10			
Rifampicin Dosing				Days 3 to 11			
Pharmacokinetics							
Blood samples for pamiparib concentration			X (30 min predose, 0.5, 1, 2, 4, 6, 9, 12, 24, and 48 hours postdose)	Day 10: 30 min predose, 0.5, 1, 2, 4, 6, 9, 12, 24, and 48 hours postdose			

VV-CLIN-024656 Version 1.0

Schedule of Assessments: Part A (Continued)

Study Procedures	Screening		Core Phase				Safety Follow-Up Visit (≤30 days after last dose) ^p
	Days -28 to -1 ⁿ	Day -1	Day 1	Days 2 to 11	Day 12	Core Phase EOT Visit (≤7 days after last dose)	
Safety and tolerability							
Adverse event recording	X	X	X	X	X	X	X
Prior/concomitant medication recording	X	X	X	X	X	X	X
Clinical chemistry, hematology and urinalysis ^h	X	X			X	X	X
Vital signs ⁱ	X	X	X (30 min predose and 1, 2, 4, and 24 hours postdose)	Day 10: 30 min predose and 1, 2, 4, and 24 hours postdose	X	X	X
12-lead ECG ^j	X		X (30 min predose and 2 hours postdose)	Day 10: 30 min predose and 2 hours postdose	X	X	
Complete physical examination ^k	X	X					
Limited physical examination ^l			X	X (Day 10)	X	X	X
CT or MRI ^m	X						

Abbreviations: BMI = body mass index; CT = computed tomography; ECOG = Eastern Cooperative Oncology Group; ECG = electrocardiogram; EOT: end of treatment; FSH = follicle-stimulating hormone; MRI = magnetic resonance imaging; PK = pharmacokinetic; SAE = serious adverse event.

- a. Confirmation of eligibility: all laboratory values obtained on Day -1 must meet eligibility criteria.
- b. Demographic data: Date of birth, gender, ethnicity, and race must be recorded.

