- m. A computed tomography (CT) or MRI scan of the thorax, abdomen, and pelvis plus other relevant evaluations as appropriate will be performed at Screening.
- n. All assessments obtained within 3 days of Day -1 do not have to be repeated on Day -1.
- o. Check-out takes place on Day 12 after all procedures have been completed.
- p. All patients, including those who withdraw early from the study, will have an EOT visit within 7 days after the last dose of rifampicin. Safety Follow-up in the Core Phase is only to be conducted if the patient does not continue to the Extension Phase. All patients who permanently discontinue study drug will have a Safety follow-up approximately 30 days after the last day of study drug or before initiation of new anticancer therapy, whichever occurs first. AEs and SAEs will be collected; clinical laboratory assessment should only be conducted if the patient had an ongoing clinical laboratory abnormality in the previous visit, which the PI considers to be related to study drug. If no laboratory assessments are required, the patient should be contacted by telephone for a review of AEs/concomitant medications and the limited physical exam will not be performed.

Schedule of Assessments: Part B

Study Procedures	Screening	Core Phase					Safety Follow-Up Visit (≤30 days after last dose) ^p
		Day of Phase	Days -28 to -1 ⁿ	Day -1	Day 1	Days 2 to 8	
Informed consent	X						
Inclusion/exclusion criteria	X						
Confirm eligibility (laboratory values) ^a		X					
Demographic data ^b	X						
Medical history ^c	X						
ECOG Performance Status	X						
Urine drug screen	X	X					
Alcohol breath test	X	X					
Serum pregnancy test/ FSH ^d	X (Days -7 to -1)						
Height, BMI ^e	X						
Weight	X	X				X	
Serology (HBV, HCV) ^f	X						
Study residence							
Check-in		X					
Check-out						X ^o	
Non-residential visit							X
Study drug administration^g							
Pamiparib Dosing			X	Day 7			
Itraconazole Dosing				Days 3 to 8			
Pharmacokinetics							
Blood samples for pamiparib concentration			X (30 min predose, 0.5, 1, 2, 4, 6, 9, 12, 24, and 48 hours postdose)	Day 7:30 min predose, 0.5, 1, 2, 4, 6, 9, 12, 24, and 48 hours postdose			

VV-CLIN-024656 Version 1.0

Schedule of Assessments: Part B (Continued)

Study Phase	Screening	Core Phase					Safety Follow-Up Visit (≤30 days after last dose) ^p
Day of Phase	Days -28 to -1 ⁿ	Day -1	Day 1	Days 2 to 8	Day 9	Core Phase EOT Visit (≤7 days after last dose)	
Safety and tolerability							

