- g. End-of-Treatment (EOT) Visit: To occur within 7 days after the last day of study drug administration. A visit should be scheduled as soon as possible, but may occur later after discussion with the medical monitor for specific circumstances, such as prolonged hospitalization. An ECG does not need to occur at the EOT Visit if one was performed within 14 days prior to the visit.
- h. Safety Follow-up Visit: To occur approximately 30 days after the last day of study drug administration or before initiation of new anticancer therapy, whichever occurs first. If new anticancer therapy is initiated before this safety follow-up, a safety follow-up should be scheduled as soon as possible. Clinical laboratory evaluations are only required if the patient had an ongoing clinical laboratory abnormality at the previous visit that the principal investigator considered to be related to study drug. For patients who do not want to or cannot return to the clinic for the safety follow-up, the patient should be contacted by telephone for a review of adverse events.
- i. Cycle 1 Day 1: Assessments will be conducted prior to first dosing in the Extension Phase.
- j. Follow-up assessments: only to be conducted if the patient has an ongoing laboratory abnormality at the previous visit that the PI considers to be related to the study drug.

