9.2.3 Other Definitions

General definitions for variables as used in the text.

Change from baseline will be calculated for safety measures, see below.

Variable	Dataset	Definition/Calculation
Change from Baseline	All	Post-dose Observation minus Baseline Observation
Study Day (Prior to first dose day)	All	Date of Measurement minus Dose Date
Study Day (Predose on first dose day and post first dose)	All	Date of Measurement minus Dose Date +1
TEAE	AE	AE is a TEAE if the AE with an onset date on or after the date of first dose of study medication until the date of last study medication dose plus 30 days.

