18.1.1 Adverse Events

Adverse events will be classified using the Medical Dictionary for Regulatory Activities (MedDRA) classification system.

All adverse events (including non-treatment-emergent events) recorded on the CRF will be listed.

All AE summaries will include only treatment-emergent adverse events. Treatment-emergent adverse events are those AEs with an onset date on or after the date of first dose of study medication until the date of last study medication dose plus 30 days.

AEs will be categorized according to the following:

- Prior to Day 1 (thus not summarized, just listed)
- From Day 1 to the day prior to start rifampin or itraconazole dosing (category = pamiparib only)
- Part A: The day of start of rifampin dosing to the day prior to combined pamiparib and rifampin dosing (category = rifampin)
- Part A: At or after the day of coadministration until date of last dosing in core phase plus 30 days and before the administration of pamiparib in the Extension Phase (category = pamiparib with rifampin)

- Part B: The day of start of itraconazole dosing to the day prior to combined pamiparib and itraconazole dosing (category = itraconazole)
- Part B: At or after the day of coadministration until date of last dosing in core phase plus 30 days and before the administration of pamiparib in the Extension Phase (category = pamiparib with itraconazole)
- Extension Phase AEs

An overview of all AE will present the following frequencies by treatment and part:

- All treatment-emergent AEs
- Grade 3 or greater treatment-emergent AEs
- Treatment-related, treatment-emergent AEs
- Serious treatment-emergent AEs
- Serious, treatment-related treatment-emergent AEs
- Treatment-emergent AEs with an outcome of death
- Treatment-emergent AEs leading to discontinuation of study treatment

A breakdown of the number and percentage of patients reporting each adverse event, categorized by body system and preferred term, will be presented. Counting will be done by patient only, not by event; patients will only be counted once within each body system or preferred term.

A summary of drug related events reported, categorized by relationship to either study drug, will be provided. Patients with multiple events within a particular body system or preferred term will be counted once for a relation to study drug within that body system or preferred term.

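### The final Safety Follow-up may fall up to 7 days before the 30-day adverse event window closes, leaving those days without a planned AE inquiry

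*Protocol*

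**What the plan says.** **When the last contact takes place.** Protocol Section 8.4: "The Safety Follow-Up visit will occur 30 days (± 7 days) after the last dose of study drug", or before new anticancer therapy if that comes first. The synopsis gives the same ± 7 days, and so does Section 4.1 for the Core Phase. The column headers of the Appendix 1 schedules read "Safety Follow-up Visit (≤30 days after last dose". The footnotes differ from the headers. In the Part A and Part B schedules, footnote p speaks of a "Safety follow-up approximately 30 days after the last day of study drug or before initiation of new anticancer therapy, whichever occurs first". For the Extension Phase, footnote h says: "To occur approximately 30 days after the last day of study drug administration or before initiation of new anticancer therapy, whichever occurs first". SAP Appendix 2 reproduces these schedules.

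**How long AEs are counted.** Under Protocol Section 9.3.1, AEs and SAEs "will be reported until 30 days after the last dose of study drug or initiation of new anticancer therapy, whichever occurs first". SAP Section 9.2.3 counts an AE as treatment-emergent "until the date of last study medication dose plus 30 days", and SAP Section 18.1.1 repeats this window.

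**When patients are asked about AEs.** Protocol Section 8.2.1 has patients questioned "at least once each day while a resident at the study site and at each study visit". At other times reporting is spontaneous. The schedules have no column after the Safety Follow-up.

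**The concern.** The visit window is symmetric around the day on which AE counting stops. A site that follows the protocol exactly can put its last AE question to a patient up to a week before the counting window ends. Section 9.3.1 adds that, once a patient is discontinued from the study, investigators need not actively look for further AEs.

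Incidence and severity of AEs are secondary endpoints. The SAP reports the number and percentage of patients with treatment-emergent AEs and plans no adjustment for how long each patient was actually questioned. An event that is never elicited can only lower the count. With about 12 patients per part, one patient is 1/12, or about 8 percentage points. That figure shows how coarse the percentages are; it does not predict a loss of that size.

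**Working it through.** The documents state no figure for this gap, so there is none to reproduce. The check is day arithmetic. All days below are days after the last dose, not study days.

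**Inputs**
- Nominal visit day 30, tolerance 7 days (Protocol Section 8.4, synopsis, Section 4.1).
- End of the AE window: day 30 (Protocol Section 9.3.1; SAP Sections 9.2.3 and 18.1.1).
- No planned contact after the visit (Protocol Appendix 1).

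**Permitted visit days.** Earliest 30 − 7 = 23; latest 30 + 7 = 37. That is 37 − 23 + 1 = 15 days.

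**Gap.** Days without a planned inquiry = max(0, 30 − visit day).

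| Visit day | 23 | 24 | 25 | 26 | 27 | 28 | 29 | 30 to 37 |
|---|---|---|---|---|---|---|---|---|
| Gap (days) | 7 | 6 | 5 | 4 | 3 | 2 | 1 | 0 |

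- Worst case: 7/30 = 23% of the post-dose window (days 24 to 30).
- Permitted days with a gap: 7 of 15. Without a gap: 8 of 15.
- If visits were spread evenly over the 15 days (an assumption; the documents give no distribution), the mean gap would be (7+6+5+4+3+2+1)/15 = 28/15 = 1.9 days, about 6% of the window.

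**Who is exposed.** The gap concerns the last follow-up only. Patients who enter the Extension Phase have no Core Phase Safety Follow-up, but AEs are recorded at their Extension visits. The SAP also closes the core-phase AE category before the first Extension dose.

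**New anticancer therapy.** The protocol's reporting period ends when such therapy starts, so a visit brought forward for that reason leaves no gap in the protocol period. The SAP's treatment-emergent definition has no such cut and still runs to 30 days. This is a separate difference in definition and is not counted above.

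**The timing statements side by side**

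| Place | Permitted timing |
|---|---|
| Section 8.4, synopsis, Section 4.1 (Core Phase) | days 23 to 37 |
| Appendix 1 headers, copied in SAP Appendix 2 | day 30 or earlier; no lower limit |
| Appendix 1 footnotes p and h, copied in SAP Appendix 2 | about day 30 |

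The header excludes days 31 to 37, which Section 8.4 allows. These are also days on which no gap arises.

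**With the fix.** For every visit day from 30 to 37, max(0, 30 − visit day) = 0.

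**The case against.** The strongest reply is that little is lost. Section 9.3.1 requires AEs to be reported to day 30, and nothing says that an early visit cancels that duty. The sentence about not actively seeking AEs comes later and concerns patients already discontinued from the study. Patients are encouraged to report spontaneously (Section 8.2.1), ongoing AEs are followed (Section 9.1.4), and related SAEs remain reportable after the window. All of this stands: the gap is in planned questioning, not in the duty to report.

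A second reply is pharmacological. The terminal half-life in Protocol Section 1.2.1.1 is about 13 hours, range 5.5 to 34. Day 23 is 23 × 24 = 552 hours after the last dose, and 552/34 is about 16 half-lives even at the longest value. New exposure-related events on days 24 to 30 should therefore be few. This supports a low severity. It does not remove the mismatch, because the plan itself chose to count to day 30 regardless of relationship to drug.

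Two stronger readings are tempting, and the documents do not support them.
- A reader might infer from the schedule header that the visit may fall on any day up to 30, so that the gap could be much longer. For example, a visit on day 8, just after the 7-day End-of-Treatment limit, would leave 30 − 8 = 22 days. The footnotes to the same schedules say about 30 days, and Section 8.4 says 30 ± 7. The header is a wording conflict, not evidence of a longer gap.
- A reader might infer that every patient is affected. Any patient can be, but 8 of the 15 permitted days leave no gap.

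**Conclusion.** The point holds as a small mismatch between data collection and counting. Under Section 8.4, a visit 23 to 29 days after the last dose leaves 1 to 7 days of the 30-day window, at most 23%, without a planned AE inquiry. A visit on days 30 to 37 leaves none. The possible effect is a slight under-count of late treatment-emergent AEs in descriptive safety summaries. Its size in events cannot be derived from the documents. The SAP plans no formal hypothesis testing, and the primary PK analysis is not touched.

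The header wording is a separate inconsistency and needs correcting whatever view one takes of the gap.

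The conclusion assumes that sites use the early half of the permitted window at least some of the time, and that no further contact is arranged outside the schedule.

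**What to change.** Either of two changes closes the gap:
1. Set the last AE contact at 30 days after the last dose with a window of +7 days only.
2. Keep ± 7 days and add a telephone AE review at or after day 30 whenever the visit was earlier.

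Both should keep the existing exception for the start of new anticancer therapy.

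Align the wording in Protocol Section 8.4, the synopsis, Section 4.1, the headers and footnotes of the three Appendix 1 schedules, and their copies in SAP Appendix 2.

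**Cost.** Edits in those places, and either slightly later visits or at most one extra call per patient. Section 8.4 and footnote p already accept a telephone review of AEs, so no new procedure is needed. The first option moves some visits later, which leaves more time for new therapy to start beforehand; the second avoids this.
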